1.1 Synopsis

Protocol Title: A Prospective, Randomized, Crossover Study of the TheraPAP Compared to Automatic Adjusting Positive Airway Pressure (APAP) for the Treatment of Obstructive Sleep Apnea (OSA)

Protocol Name/Number: TheraPAP Adherence 1

Sponsor: SleepRes, PLLC

Rationale: TheraPAP is a prototype device (with full documented electrical and isolation safety) being developed by SleepRes for the treatment of obstructive sleep apnea (OSA) that can deliver either standard CPAP at a set pressure or what is called TPAP¹. TPAP is a pressure control algorithm that lowers the pressure from the set pressure at the beginning of inspiration and does not return the pressure to the full set level until about halfway through expiration. The present study, TheraPAP Adherence 1, is a randomized crossover study designed to examine the difference in therapy adherence between TPAP vs. CPAP alone in the treatment of OSA.

Overall Design:

The TheraPAP Adherence Study is a randomized, crossover study in treatment naive participants with OSA in which the adherence to therapy will be compared between TPAP and standard APAP. Because all participants will breathe on both therapy types and those therapy types are individually unique in feel, blinding is not possible. Participants will be chosen from a pool of patients who are PAP-naïve and who have received either a PSG (in-lab polysomnogram), split-night study (in-lab PSG and pressure titration) or home sleep study (HST) within the previous 3 months.

Upon signing an informed consent, participants will be randomly assigned to start on either the TPAP or APAP arms when they arrive at the office to pick up their Sefam S.Box with TheraPAP algorithms integrated. Each participant will then be given their new equipment and will be trained in proper use for both arms of the study so that they will not need to appear at the office again until the study is completed. In both the APAP and TPAP arms, participants will have their therapy set to 5-20 cmH₂O for three nights. The pressure range will then be narrowed to ± 2 cmH₂O around their 95% pressure level as assessed during the third night. This same pressure range will be used during the second arm for each patient.

¹ TPAP will be used herein to refer to the active treatment.

Within the TPAP arm, participants will be set to a double Comfort Setting drop according to the following table. This drop schedule will be implemented even while the TPAP device is operating with automatic pressure adjustment.

P _{set} (cmH ₂ O)	Pressure Drop 1 (cmH ₂ O)	Pressure Drop 2 (cmH ₂ O)
5.0 - 5.9	0	0
6.0 - 6.9	1	0
7.0 - 7.9	2	0
8.0 - 8.9	2	1
9.0 - 9.9	2	2
10.0 - 20.0	2	3

Table 1: Comfort Setting Pressure Drops 1 and 2 to be used at the specified target set pressure to the patient.

Participants will use their starting therapy nightly at home for 6 weeks after which time they will undergo a washout period of 1 week where no therapy will be used. Following the washout period, they will initiate another 6-week usage with the second therapy. Afterward, they will return to the office to receive their permanent equipment. Phone calls as reminders to end the first arm, start the washout period, then to start the second arm will be made.

Immediately after both arms of the study are completed, the following will occur:

- Eligibility criteria will be reviewed and confirmed
- Participants will be asked to respond to the following
 - ESS (Epworth Sleepiness Scale)
 - FOSQ (Functional Outcomes of Sleep Questionnaire)

During the home use period, subjects will be called at the following time points during each arm of the study. At each time point, adverse events and compliance with the device will be assessed. Subjects using the device less than an average of 5 hours per night during the first week will be contacted on a more regular basis (weekly until 5 hour per night use is achieved) to address any problems and encourage use. If patients discontinue use of the device during the home use period, they will still be encouraged to return for all testing per protocol. If a patient refuses to come in for further testing, they will be considered a lost to follow up and excluded from efficacy analysis.

- 1 Day Phone Call (+2 days)
- 7 Day Phone Call (+/- 3 days)
- 14 Day Phone Call (+/- 3 days) IF deemed necessary per 7 Day compliance
- 28 Day Phone Call (+/- 3 days) Check-in

- Week 6 Phone Call (+/- 3 days) – End first arm, fill out questionnaires, start Washout Period
- Week 7 Phone Call (+/- 3 days) - Review protocol, start 2nd arm
- Week 12 (+/- 3 days) - Equipment Return

Data collected from the therapy device will include the following:

- Usage averaged over the 6-week period and nightly
- Leak averaged over the 6-week period and nightly
- P95 averaged over the 6-week period and nightly (for the CPAP/APAP arm only)
- Sleep events averaged over the 6-week period and nightly

Number of Participants:

A total of 32 participants will be enrolled.

Study Duration:

Per subject study duration will be approximately 4 months (screening plus 90 days of home use). Total study duration will be approximately 9 months (6-month enrollment plus 35 days of home use).

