4.1 Overall Design

Safety issues regarding this study are detailed in Appendix 1: Regulatory, Ethical, and Study Oversight Considerations.

The TheraPAP Adherence 1 Study is a randomized, controlled, crossover study in PAP-naïve participants with OSA. Pre-screening is conducted to establish potential eligibility based on an in-lab polysomnogram (PSG), a PSG split-night PSG/titration or a home sleep study (HST) that has been conducted within the previous 3 months. Participants would then be recruited as described below. For those who consent, they will be given the equipment and instructions to complete both arms of the study but will have their therapy device set to the parameters necessary to start the first arm, which will be randomly assigned. They will use the device nightly for 6 weeks, after which they will use no therapy for 1 full week (washout period). During this washout period, their therapy device will be remotely set to their second arm. When they restart therapy, they will use the device nightly for a further 6 weeks. During each arm, various data will be remotely collected from their therapy device, and after completion of each arm, they will fill out 3 questionnaires and average data during the 6 weeks of that arm will be downloaded. Once all activities are completed, they will be eligible to receive the incentive pay and their involvement will be completed.

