4.2.3 Second 6-Week Arm

Following the one-week washout period, patients will start the second arm therapy for the next six weeks of nightly use. The procedure will be exactly the same as for the first arm, described above except that the device pressure range will be retained at the same settings that were present during the bulk of the first arm.

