4.3 End of Study Definition

Once the second 6-week arm is over and questionnaires have been completed, the patients will return their equipment to the office. Once the equipment is returned, the participants' involvement in the study will be complete and they will be able to receive their study incentive. They will also then be given their regular take-home equipment with usage instructions.

5 Study Population

Eligible participants will be recruited from the pool of PAP-naïve patients who have undergone some form of sleep study and will be receiving CPAP therapy equipment.

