Records and documents, including signed ICF, pertaining to the conduct of this study must be retained by the Investigator for 5 years after study completion unless local regulations or institutional policies require a longer retention period. No records may be destroyed during the retention period without the written approval of the Sponsor. No records may be transferred to another location or party without written notification to the Sponsor.

All data generated by the site personnel will be captured and stored in an internal password-protected system.

6 Source Documents

Source documents provide evidence for the existence of the participant and substantiate the integrity of the data collected. Source documents are filed at the site.

7 Publication Policy

The Sponsor will generally support publication, reserving the right to review prior to submission.

Authorship will be determined by mutual agreement and in line with the International Committee of Medical Journal Editors' authorship requirements.

A summary of the study results will also be posted in a publicly accessible database (e.g., www.ClinTrials.gov).

8 Protocol Approval and Amendment

Before the start of the study, the study protocol and/or other relevant documents will be approved by the IRB/Competent Authorities, in accordance with local legal requirements. The Sponsor must ensure that all ethical and legal requirements have been met before the first participant is enrolled in the study.

This protocol is to be followed exactly. To alter the protocol, amendments must be written, receive approval from the appropriate personnel, and receive IRB/Competent Authority approval prior to implementation (if appropriate). Any deviations from the protocol will be reported to the Sponsor as Protocol Deviations.

Administrative changes (not affecting the participant benefit/risk ratio) may be made without the need for a formal amendment. All amendments will be distributed to all protocol recipients, with appropriate instructions.

9 Liability and Insurance

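### Equipment return at Week 12 cuts the 6-week second arm to about 35 days on a calendar count, and the 35 days of home use in the total-duration sentence is wrong

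*Protocol*

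**What the plan says.** Several sections give the second arm a length of six weeks. The Synopsis describes a 6-week arm, a 1-week washout and another 6-week arm. Section 4.1 says that after the washout "they will use the device nightly for a further 6 weeks". Section 4.2.3 says "patients will start the second arm therapy for the next six weeks of nightly use". Section 4.3 ties the end of participation to that length: "Once the second 6-week arm is over and questionnaires have been completed, the patients will return their equipment to the office".

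The contact schedule in the Synopsis attaches week numbers to these steps. The Week 6 call ends the first arm and starts the washout. The next entry is "Week 7 Phone Call (+/- 3 days) - Review protocol, start 2nd arm", and the last is "Week 12 (+/- 3 days) - Equipment Return". The schedule does not say from which day its weeks are counted.

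The Study Duration paragraph of the Synopsis has two sentences. The first reads "Per subject study duration will be approximately 4 months (screening plus 90 days of home use" (closing bracket omitted). The second reads "Total study duration will be approximately 9 months (6-month enrollment plus 35 days of home use" (likewise).

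**The concern.** There are two separate slips.

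The first concerns an operative date. Week 12 is the only numbered week attached to the close of the second arm; the contact schedule repeated in Section 4.2.2 stops at the Day 28 call. Device usage is the primary endpoint and is averaged over each 6-week period, and collection ends when the device is handed back. A coordinator who books the return visit from the contact list, counting calendar weeks, would end period 2 about a week early. The two periods would then cover different lengths of follow-up, with a possible period effect. The shortening would fall on period 2 in both sequences, so it would not bias the treatment comparison directly if the sequences are balanced or period is in the model.

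The second is the home-use figure in the total-duration sentence. It contradicts the sentence before it and does not produce the total it is meant to explain.

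**Working it through.** **Inputs**, all from the protocol:
- Arm 1: 6 weeks; washout: 1 week; arm 2: 6 weeks (Synopsis; Sections 4.1 and 4.2.3).
- Contact schedule: arm 1 ends at Week 6, arm 2 starts at Week 7, equipment is returned at Week 12, each with a window of 3 days either way (Synopsis).
- Home use: 90 days per subject, about 4 months with screening (Synopsis, Study Duration).
- Total duration: about 9 months, from 6 months of enrolment plus 35 days (Synopsis, Study Duration).

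Conversions: 7 days per week and 365.25 / 12 = 30.44 days per month.

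**1. Length of the full course**

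42 + 7 + 42 = 91 days = 13 weeks. Of these, 84 are therapy days and 7 are washout.

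**2. The plan's own total duration**

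| Home use added to 6 months | Calculation | Total |
|---|---|---|
| 35 days (as stated) | 6 + 35/30.44 | 7.15 months |
| 90 days (per-subject sentence) | 6 + 90/30.44 | 8.96 months |
| 91 days (design) | 6 + 91/30.44 | 8.99 months |

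The stated 9 months is not reproduced with 35 days; the sum falls about 1.85 months short. It is reproduced with 90 or 91 days. The per-subject sentence is coherent: 4 months is 121.75 days, which leaves about 32 days for screening after 90 days of home use. The 35 is therefore the wrong figure, and the 9 months is right.

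**3. Length of the second arm from the contact schedule, calendar count**

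Week 7 is day 49 and Week 12 is day 84.

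| Case | Calculation | Days for arm 2 | Short of 42 by |
|---|---|---|---|
| Nominal dates | 84 − 49 | 35 | 7 (7/42 = 17%) |
| Start 3 days early, return 3 days late | 87 − 46 | 41 | 1 (1/42 = 2%) |
| Start 3 days late, return 3 days early | 81 − 52 | 29 | 13 (13/42 = 31%) |

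Even the most favourable use of both windows does not reach 42 days.

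**4. The alternative count**

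If only weeks on therapy are numbered, arm 1 is Weeks 1 to 6 and arm 2 is Weeks 7 to 12. Therapy days 43 to 84 then give 84 − 43 + 1 = 42 days, and the conflict disappears.

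**5. After correction**

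With return at Week 13 (day 91), 91 − 49 = 42 days. A 3-day window on both sides would still allow (91 − 3) − (49 + 3) = 36 days, so the corrected entry also needs a minimum of 42 nights from the actual start.

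**The case against.** The strongest reply is that the Week 12 entry conflicts with a 6-week second arm only under a counting rule the protocol never states. Numbered by weeks on therapy, the schedule gives exactly 6 + 6. This is possible, but it fits poorly. The list puts one week between the start of washout and the start of the second arm, which is the calendar length of the washout. On a therapy-only count no numbered time passes between those two calls, so Week 6 would have to mean the end of a week and Week 7 the beginning of one. The 90 days per subject also matches a 13-week calendar that includes the washout, not 12 weeks (84 days). Even if the therapy-only count was meant, the list gives no origin, so Week 12 can reasonably be read as day 84.

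A second reply is that the operative rule is clear elsewhere. Section 4.3 places return after the full second arm. The Schedule of Activities (Section 1.2) lists return among the activities that follow the second 6-week period, and Section 6 refers to that schedule for timing. Appendix 1, item 8 says "This protocol is to be followed exactly", but that binds staff to these sections as much as to the contact list. This stands: the Week 12 entry is the outlier, and staff who follow the other sections lose no data.

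A third reply is that an average over 35 nights estimates nearly the same quantity as one over 42, and that the sample size calculation in Section 7.1 does not depend on the number of nights. The sample-size point is correct, and no bias in the treatment comparison is claimed. These arguments limit the importance of the point but do not make the date right.

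For the 35 days there is no defence. No way of counting weeks reconciles it with 90 days or with 9 months. It is, however, a planning figure that sets no visit and no analysis.

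**Conclusion.** The concern holds, as a minor inconsistency.

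- **35 days of home use: certain.** It contradicts the preceding sentence and gives 7.1 months where 9 is stated; 91 days gives 9.0. It has no effect on the analysis.
- **Week 12 return: wrong on a calendar count, which is the better-supported reading, and ambiguous otherwise.** Followed literally, it gives period 2 about 35 nights instead of 42, a loss of 7 nights or 17%; at the extremes of both windows the loss is 1 to 13 nights (2% to 31%).

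The lost nights are conditional on two things: that weeks are calendar weeks from the first night of the first arm, and that staff act on the contact list and not on Section 4.3 and the Schedule of Activities. If either fails, the loss is zero and only the text needs correcting.

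**What to change.** - In the contact schedule, move equipment return to Week 13 (day 91), and add that it must not take place before 42 nights from the actual start of the second arm.
- State that weeks are counted from the first night of the first arm.
- In the total-duration sentence, replace 35 days with about 91 days (13 weeks, including the 1-week washout), and use the same 6 + 1 + 6-week timeline wherever durations are given.

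The cost is a text correction to one schedule entry and one duration sentence. No procedures are added, and the second arm keeps the six weeks already planned.

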7.1 Sample Size Determination

Sample sizes are estimated to achieve 80% power based on a 1-sided 5% significance level. As this is an exploratory proof of concept trial, a 1-sided 5% significance level was selected. The within subject standard deviation is assumed to be 1 hour and the minimum treatment difference is assumed to be 0.5 hours.

When there are 2 treatments and a sample size of 14 in each of the 2 sequences, a 2x2 Williams Crossover Design will have approximately 82% power to detect a minimum pairwise difference of 0.5 or greater, assuming that the standard deviation of the paired differences is 1 at a one-sided 5% significance level.

Assuming ~20% dropout and total of 36 patients (18/sequence) is planned.

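### The synopsis enrols 32 participants but section 7.1 plans 36, and only 36 follows from the protocol's own sample-size assumptions

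*Protocol*

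**What the plan says.** The Number of Participants entry in the synopsis (Protocol section 1.1) reads "A total of 32 participants will be enrolled".

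Protocol section 7.1 (Sample Size Determination) ends with a different total: "Assuming ~20% dropout and total of 36 patients (18/sequence) is planned". It reaches that total as follows:

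- Target: "Sample sizes are estimated to achieve 80% power based on a 1-sided 5% significance level".
- Evaluable sample: "When there are 2 treatments and a sample size of 14 in each of the 2 sequences", that is, 28 in all.
- Result: the design "will have approximately 82% power to detect a minimum pairwise difference of 0.5 or greater". For this calculation the paired differences are given an SD of 1.

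Both totals are in current text, and nothing elsewhere in the protocol explains or reconciles them.

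**The concern.** The two figures cannot be read as enrolled versus evaluable. The synopsis figure of 32 is expressly an enrolment figure, and the evaluable number in section 7.1 is 28. They are two targets for the same quantity.

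Three things are at stake:

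- **When recruitment ends.** A site working from the synopsis stops four participants before one working from section 7.1. Appendix 1 (section 8) requires the protocol to be followed exactly, and no enrolment total satisfies both statements.
- **Power.** The allowance for dropout above the 28 needed falls from eight (36 − 28) to four (32 − 28). Attrition matters here, because the synopsis and section 4.2.2 remove from the efficacy analysis participants who refuse further testing or surveys.
- **A fixed stopping point.** The trial is open-label, and usage, the primary endpoint, is collected remotely every day (section 4.2.2) and stored at the sponsor's office (section 6.1). Two documented totals leave a choice about when to stop that one total would remove.

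**Working it through.** **Inputs, all from section 7.1 except the last**

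- Difference to detect: 0.5 h
- SD of the paired differences: 1 h
- Significance level: one-sided 5%
- Target power: 80%
- Evaluable: 14 per sequence × 2 = 28
- Dropout: about 20%
- Enrolment: 36 (section 7.1) or 32 (synopsis)

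**Step 1. Reproduce the stated power.** For a 2×2 crossover with n completers, use the noncentral t distribution with noncentrality 0.5 × √n / 1 and n − 2 degrees of freedom, at one-sided 5%. With n = 28 the noncentrality is 0.5 × √28 = 2.65 and power is **82.4%**, which matches the stated figure. A paired t-test with n − 1 degrees of freedom gives 82.5%. The normal approximation gives 84.2%, which does not match, so the protocol's figure appears to be t-based.

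**Step 2. Reproduce the enrolment total.** 28 / (1 − 0.20) = 35, rounded up to **36** so that the sequences are equal at 18 each. This is the figure in section 7.1.

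**Step 3. Test the synopsis figure against the same inputs.**

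- Expected completers: 32 × 0.80 = 25.6, so 25 to 26, which is two to three short of 28.
- Dropout at which 32 still leaves 28: 1 − 28/32 = 12.5%.
- For comparison, 36 × 0.80 = 28.8 completers, and 36 leaves 28 up to a dropout of 1 − 28/36 = 22.2%.

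**Step 4. Power at each number of completers** (same method as step 1):

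| Completers | Power, t-based | Power, normal approximation |
|---|---|---|
| 25 | 78.2% | 80.4% |
| 26 | 79.7% | 81.7% |
| 27 | 81.1% | 83.0% |
| 28 | 82.4% | 84.2% |
| 29 | 83.6% | 85.3% |

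The smallest number of completers that reaches 80% by the t-based method is 27. With 32 enrolled, that allows a dropout of 1 − 27/32 = 15.6%.

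**A separate matter.** Section 7.1 also says "The within subject standard deviation is assumed to be 1 hour and the minimum treatment difference is assumed to be 0.5 hours". If 1 h is the within-subject SD of a single period, the SD of the differences is √2 × 1 = 1.41 h. Power is then about 57% with 28 completers and about 53% to 54% with 25 to 26. Almost all of that drop comes from the SD, and the enrolment conflict accounts for only 3 to 4 points of it. It needs its own clarification and is not counted in the size of this point.

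**The case against.** The contradiction and the arithmetic are hard to dispute. The case on the other side is about how much they matter.

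- **The power loss is very small.** At 26 completers, the nearest whole number to 25.6, the shortfall from 80% is 0.3 points, and at 25 it is 1.8 points. By the normal approximation there is no shortfall. The dropout rate is itself approximate: at about 16%, 32 enrolled leaves about 27 completers (32 × 0.84 = 26.9) and 81.1% power. Section 7.1 describes the trial as exploratory, and a deficit under two points would hardly change how its result is read. This stands, except that the normal approximation does not reproduce the protocol's own 82% and so is not the natural yardstick.
- **The stopping-point argument is thin.** Section 7.4 plans no interim analysis, and the daily usage data are described as serving later analysis and contact with participants. No section describes a comparison between treatments before enrolment ends, and the range is only four participants. This largely stands: the risk is possible in principle but neither shown nor quantified.

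Neither argument removes the need to reconcile the two totals.

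**Conclusion.** The point holds. The protocol states two different enrolment totals, and only 36 is consistent with its own 28 evaluable participants and roughly 20% dropout.

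If recruitment stops at 32 and dropout is 20%, power falls from about 82% to between 78.2% and 79.7%. That is a loss of about 3 to 4 points and a slight miss of the 80% target. These figures assume a difference of 0.5 h, an SD of paired differences of 1 h, a one-sided 5% level and a t-based calculation.

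The reason to correct this is the contradiction in a figure that governs conduct of the trial. The loss of power is secondary.

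**What to change.** State one enrolment total in both places. There are two ways to do it:

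1. Change the synopsis to 36 (18 per sequence), the number that section 7.1 derives. This costs one edited number and, for a site that had planned on 32, four more participants.
2. Keep 32 and rewrite the end of section 7.1 as 16 per sequence, 25 to 26 expected completers at 20% dropout, and about 78% to 80% power. The text should then say that this is at or just below the 80% target, or the protocol should justify a lower dropout assumption. Dropout of no more than 15.6% would keep 80% power, and no more than 12.5% would keep the stated 82%.

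The first is simpler, because it leaves the rest of section 7.1 unchanged. Neither option alters the design or the treatments.
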